8.10.2 Samples for Research Biosample Repository

8.10.2.1 Overview of the Research Biosample Repository

The Research Biosample Repository (RBR) is a centrally administered group of facilities used for the long-term storage of human biological specimens, including body fluids, solid tissues, and derivatives thereof (e.g., DNA, RNA, proteins, peptides). The collection, storage, and analysis of RBR samples will facilitate the rational design of new pharmaceutical agents and the development of diagnostic tests, which may allow for individualized drug therapy for participants in the future.

Samples for the RBR will be collected from participants who give specific consent to participate in this optional research. RBR samples will be analyzed to achieve one or more of the following objectives:

- To study the association of biomarkers with efficacy or disease progression
- To identify safety biomarkers that are associated with susceptibility to developing adverse events or can lead to improved adverse event monitoring or investigation
- To increase knowledge and understanding of disease biology and drug safety

- To study drug response, including drug effects and the processes of drug absorption and disposition
- To develop biomarker or diagnostic assays and establish the performance characteristics of these assays

8.10.3 Approval by the Institutional Review Board or Ethics Committee

Collection, storage, and analysis of RBR samples is contingent upon the review and approval of the exploratory research and the RBR portion of the Informed Consent Form by each site's IRB/EC and, if applicable, an appropriate regulatory body. If a site has not been granted approval for RBR sampling, this section of the protocol (Section [8.10.6](#)) will not be applicable at that site.

8.10.4 Sample Collection

The following samples will be stored in the RBR and used for research purposes, including, but not limited to, research on biomarkers related to fenebrutinib, diseases, or drug safety:

- Plasma samples collected as indicated in the schedule of activities
- Serum samples collected as indicated in the schedule of activities
- RNA samples collected as indicated in the schedule of activities
- DNA sample collected as indicated in the schedule of activities
- Leftover blood, serum, plasma, cerebrospinal fluid, and any derivatives thereof (e.g., DNA, RNA, proteins, peptides)

The above samples may be sent to one or more laboratories for analysis of germline or somatic variants via WGS, WES, or other genomic analysis methods. Genomics is increasingly informing researcher's understanding of disease pathobiology. The WGS and WES provide a comprehensive characterization of the genome and exome, respectively, and, along with clinical data collected in this study, may increase the opportunity for developing new therapeutic approaches or new methods for monitoring efficacy and safety or predicting which participants are more likely to respond to a drug or develop adverse events.

Data generated from RBR samples will be analyzed in the context of this study but may also be explored in aggregate with data from other studies. The availability of a larger dataset will assist in identification and characterization of important biomarkers and pathways to support future drug development.

For sampling procedures, storage conditions, and shipment instructions, see the laboratory manual.

All RBR samples are to be stored until they are no longer needed or until they are exhausted. However, the RBR storage period will be in accordance with the

IRB/EC–approved Informed Consent Form and applicable laws (e.g., health authority requirements).

8.10.5 Confidentiality

All RBR samples and associated data will be labeled with a unique participant identification number.

Participant medical information associated with RBR samples is confidential and may be disclosed to third parties only as permitted by the Informed Consent Form (or separate authorization for use and disclosure of personal health information) signed by the participant, unless permitted or required by law.

Given the complexity and exploratory nature of the analyses of RBR samples, data derived from these analyses will generally not be provided to study investigators or participants unless required by law. The aggregate results of any conducted research will be available in accordance with the effective Sponsor policy on study data publication.

Data generated from RBR samples must be available for inspection upon request by representatives of national and local health authorities, and Sponsor monitors, representatives, and collaborators, as appropriate.

Any inventions and resulting patents, improvements, and/or know-how originating from the use of the RBR data will become and remain the exclusive and unburdened property of the Sponsor, except where agreed otherwise.

8.10.6 Consent to Participate in the Research Biosample Repository

The Informed Consent Form will contain a separate section that addresses participation in the RBR. The investigator or authorized designee will explain to each participant the objectives, methods, and potential hazards of participation in the RBR. Participants will be told that they are free to choose not to provide optional RBR samples and may withdraw their consent at any time and for any reason during the storage period. A separate, specific signature will be required to document a participant's agreement to provide optional RBR samples. Participants who choose not to provide optional RBR samples will not provide a separate signature. The investigator should document whether or not the participant has given consent to provide optional RBR samples and (if applicable) the date(s) of consent, by completing the Sample Informed Consent/Withdrawal eCRF.

In the event of an RBR participant's death or loss of competence, the participant's samples and data will continue to be used as part of the RBR research.

8.10.7 Withdrawal from the Research Biosample Repository

Participants who give consent to provide RBR samples have the right to withdraw their consent at any time for any reason. After withdrawal of consent, any remaining samples will be destroyed. However, if RBR samples have been tested prior to withdrawal of consent, results from those tests will remain as part of the overall research data. If a patient wishes to withdraw consent to the testing of his or her RBR samples during the study, the investigator must inform the Medical Monitor in writing of the patient's wishes through use of the appropriate RBR Subject Withdrawal Form and must enter the date of withdrawal on the Sample Informed Consent/Withdrawal eCRF. If a patient wishes to withdraw consent to the testing of his or her RBR samples after closure of the site, the investigator must inform the Sponsor by emailing the study number and patient number to the following email address:

[contact]

A patient's withdrawal from this study does not, by itself, constitute withdrawal of consent for testing of RBR samples. Likewise, a patient's withdrawal of consent for testing of RBR samples does not constitute withdrawal from this study.

8.10.8 Monitoring and Oversight

All RBR samples will be tracked in a manner consistent with Good Clinical Practice by a quality-controlled, auditable, and appropriately validated laboratory information management system, to ensure compliance with data confidentiality as well as adherence to authorized use of samples as specified in this protocol and in the Informed Consent Form. Sponsor monitors and auditors will have direct access to appropriate parts of records relating to an individual's participation in the RBR for the purposes of verifying the data provided to the Sponsor. The site will permit monitoring, audits, IRB/EC review, and health authority inspections by providing direct access to source data and documents related to the RBR samples.

9. STATISTICAL CONSIDERATIONS

The primary analysis will be performed after the last patient completes the Week 12 visit or withdraws. The analysis will be performed by the Sponsor. Significance testing of the primary and secondary endpoints will account for multiplicity and control family-wise type I error. All hypothesis tests will be 2-sided unless otherwise specified.

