9.4 STATISTICAL ANALYSES

The Statistical Analysis Plan (SAP) will be finalized prior to unblinding and database lock for the primary analysis, and it will include a more technical and detailed description of the statistical analyses described in this section. This section is a summary of the planned statistical analyses of the most important endpoints, including primary and key secondary endpoints.

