## 1. INTRODUCTION

Study GN43271 is a Phase II study to assess the efficacy, safety, and pharmacokinetics of fenebrutinib, a highly selective, orally administered, adenosine triphosphate (ATP)-competitive, reversible inhibitor of Bruton’s tyrosine kinase (BTK), compared with placebo in participants with relapsing multiple sclerosis (RMS). This Statistical Analysis Plan (SAP) provides details of the planned analyses and statistical method for the study and supersedes analysis details specified in the protocol.

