#### **5.3.1 Definition of Primary Endpoint(s)**

The primary endpoint will be tested using a two-sided significance level of 0.05.

Radiologic evaluation for the primary efficacy parameter will be performed using a standardized MRI protocol at screening, and at Weeks 4, 8, and 12. All MRI scans will be read by a centralized reading center for efficacy endpoints. The centralized reading center will be blinded to treatment assignment, and the reading will be performed in the absence of clinical information. All MRI scans will also be reviewed locally by a radiologist for safety, and a MRI scan report containing only non-MS pathology will be provided to the treating investigator.

The total number of new gadolinium-enhancing T1 lesions will be calculated as the sum of the individual number of new lesions observed at Weeks 4, 8 and 12.

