#### **5.3.2 Main Analytical Approach for Primary Endpoint(s)**

The primary estimand follows a hypothetical strategy and estimates the treatment effect of fenebrutinib versus placebo had the patient not experienced a protocol defined intercurrent event on the basis of the following attributes:

- Population: all randomized participants.
- Variable: total number of new T1 Gd+ lesions as described in Section [5.3.1](#)
- Treatment:
  - 200 mg BID oral fenebrutinib
  - placebo
- Intercurrent events:
  - Withdrawal from treatment: Data after participants withdrawn from treatment will be censored, following a hypothetical strategy.
  - Initiation of another MS therapy: Initiation of another MS therapy is not allowed while on study. In case of such intercurrent event, patient will be considered as censored after initiation of another MS therapy, following a hypothetical strategy.
- Population-level-summary estimator: The total number of new T1 Gd+ lesions of primary analysis will be compared between the fenebrutinib and placebo using the negative binomial model, adjusting for stratification factor(s) (presence or absence of T1 Gd+ lesions on the screening MRI). In case of early discontinuations, different number of scans among participants may be observed. Log-transformed number of

scans will be included in the negative binomial model as an “offset” variable to account for different number of scans. The rate ratio and its two-sided 95% confidence intervals will be presented along with the p-value.

- Handling of missing data:
  - Withdrawal from study: no imputation will be conducted for missing data. The negative binomial model with number of scans as an “offset” variable accounts for different number of scans.

If the model fails to converge due to high number of zero T1 Gd+ lesion counts, a logistic regression model will be performed on the status of new T1 Gd+ lesion post-baseline (present or not) adjusted for the same stratification factor(s). The odds ratio and its two-sided 95% confidence intervals will be presented along with the p-value. A hypothetical strategy will be used as defined above.

Number of new T1 Gd+ lesions and proportion of participants with new T1 Gd+ lesions at each scheduled visit will be summarized by treatment groups.

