## **5.4 SECONDARY ENDPOINT(S) ANALYSIS(SES)**

### **5.4.1 Key/Confirmatory Secondary Endpoint(s)**

The secondary efficacy endpoints are:

- Total number of new or enlarging T2-weighted lesions observed on brain MRI at Weeks 4, 8, and 12.
- Proportion of participants free from any new gadolinium-enhancing T1 lesions and new or enlarging T2-weighted lesions observed on brain MRI at Weeks 4, 8, and 12.

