#### **5.4.1.1 Total number of new or enlarging T2-weighted lesions**

Total number of new or enlarging T2-weighted lesions will be calculated as the sum of the individual number of new or enlarging lesions at Weeks 4, 8, 12. The estimands for the secondary endpoint of total number of new or enlarging T2 lesions, will follow the same hypothetical strategy and have the same attributes (except for variable) as for the primary endpoint. Number of new or enlarging T2 lesions and proportion of participants with new or enlarging T2 lesions at each scheduled visit will also be summarized by treatment groups.

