#### **5.4.1.2 Proportion of Participants Free from any new Gadolinium-Enhancing T1 Lesions and new or Enlarging T2-Weighted Lesions**

The secondary endpoint of proportion of participants free from any new gadolinium-enhancing T1 lesions or new or enlarging T2-weighted lesions observed on brain MRI at Weeks 4, 8, and 12 will use a logistic regression model similar as described for the primary endpoint. A hypothetical strategy will also be used as defined in Section 5.3.2.

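### Family-wise error control is promised for the primary and secondary endpoints, but neither document specifies a procedure that delivers it

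*Protocol*

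**What the plan says.** Protocol section 9 commits the trial to error control over both endpoint families: "Significance testing of the primary and secondary endpoints will account for multiplicity and control family-wise type I error". Protocol sections 9.1 to 9.6 name no method. Section 9.4 passes the detail to the SAP, saying that "it will include a more technical and detailed description of the statistical analyses described in this section".

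SAP section 1 says that the SAP "supersedes analysis details specified in the protocol". It contains no multiplicity section and does not repeat or withdraw the protocol's promise. SAP section 2 states one null hypothesis, for the primary endpoint, at two-sided 0.05, and SAP 5.3.1 confirms it: "The primary endpoint will be tested using a two-sided significance level of 0.05".

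SAP 5.4.1, whose heading calls the endpoints key or confirmatory, lists two: the total of new or enlarging T2 lesions, and the proportion of participants free of new T1 Gd+ and new or enlarging T2 lesions. Under SAP 5.4.1.1 the estimand for the first will "have the same attributes (except for variable) as for the primary endpoint". Under SAP 5.4.1.2 the second "will use a logistic regression model similar as described for the primary endpoint". The model description that both refer back to, in SAP 5.3.2, reports an effect estimate with its interval and p-value. For the logistic model it reads: "The odds ratio and its two-sided 95% confidence intervals will be presented along with the p-value". It mentions no adjustment. SAP section 6 says that no supporting document exists.

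**The concern.** The promise names the secondary endpoints, so a level for the primary alone cannot satisfy it. The protocol defers to the SAP, the SAP is silent, and the SAP rules out a further document, so there is nowhere else for the procedure to be.

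As written, a secondary result with p below 0.05 could be reported as covered by the protocol's error control although that control was never set up. The clearest case is a secondary claim made after a non-significant primary, since nothing in the SAP forbids it. A procedure chosen after unblinding could be chosen to suit the results and would not restore the guarantee. The inference on the primary endpoint is not at risk.

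**Working it through.** **What the plan gives.** There is no family-wise error figure to reproduce. The inputs are three efficacy endpoints (one primary, two secondary), two-sided testing (Protocol section 9), level 0.05 for the primary (SAP sections 2 and 5.3.1), and no interim analysis (SAP 5.8).

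**What has to be assumed.** The level for each secondary is taken as 0.05. The test statistics are taken as normal with a common pairwise correlation r, from 0 to 0.9. The endpoints share lesions, so r = 0 is only an upper illustration.

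**Formula.** Under the global null, with z = 1.96, for k tests:

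P(any of k) = 1 − ∫ φ(w) · [Φ((z − √r·w)/√(1−r)) − Φ((−z − √r·w)/√(1−r))]^k dw

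At r = 0 this reduces to 1 − 0.95^k, that is 1 − 0.95² = 0.0975 and 1 − 0.95³ = 0.1426. The probability that a secondary is significant while the primary is not equals P(any of 3) − 0.05.

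| Pairwise r | Either secondary (k = 2) | Any of three (k = 3) | A secondary significant, primary not |
|---|---|---|---|
| 0.9 | 0.0704 | 0.0836 | 0.0836 − 0.05 = 0.0336 |
| 0.7 | 0.0835 | 0.1092 | 0.1092 − 0.05 = 0.0592 |
| 0.5 | 0.0907 | 0.1254 | 0.1254 − 0.05 = 0.0754 |
| 0 | 0.0975 | 0.1426 | 0.1426 − 0.05 = 0.0926 |

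A simulation with 2,000,000 draws at each r gave 0.0839, 0.1091, 0.1257 and 0.1426 for any of three, in the same row order. Whatever the correlation, the bounds are 2 × 0.05 = 0.10 for the two secondaries and 3 × 0.05 = 0.15 for all three.

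**With a fixed sequence.** If each test at 0.05 is allowed only after the previous one is significant, any false claim requires rejection of the first true null in the order. That has probability at most 0.05 at any correlation. Under the global null the figure is 0.050 for every r.

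**Effect on the primary's power.** The plan's sample size of 102 for at least 90% power cannot be confirmed, because no dispersion is given. Using its other inputs, the means over three scans are 3 × 0.7 = 2.1 and 0.4 × 2.1 = 0.84. After 3% dropout the arms have 68 × 0.97 = 65.96 and 34 × 0.97 = 32.98 participants. At an assumed negative binomial dispersion of 1:

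- SE² = (1/0.84 + 1)/65.96 + (1/2.1 + 1)/32.98 = 0.0780, so SE = 0.279.
- |log 0.4|/SE = 0.916/0.279 = 3.28, which gives power 0.907 at level 0.05.
- At a Bonferroni level of 0.05/3 = 0.0167, power falls to 0.813.

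A fixed sequence headed by the primary keeps the primary at 0.05 and therefore at 0.907. This comparison bears on the choice of remedy; the concern itself does not depend on it.

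**The case against.** The strongest counter-reading is that the trial has one formal hypothesis. SAP section 2 states a null for the primary only, and both documents define the trial's main purpose through that endpoint. The key/confirmatory heading may be template text, since the SAP was built on a sponsor model document. On that reading the secondaries are supportive and the protocol sentence is a leftover. This is possible, but the SAP does not say so: it neither withdraws the promise nor calls the secondary p-values descriptive. The two documents would still need to be reconciled, and the fix allows for this reading.

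It can also be said that an order exists, because the secondaries are numbered 1 and 2 in the estimand tables and appear in that order elsewhere. A numbered list does not make one test conditional on another, so it is not a testing procedure. It does make the natural sequence easy to declare.

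The percentages are conditional. The level, the equal correlation and the global null are all assumptions, and the any-of-three column includes the primary's own 5%. This stands, and the secondary-only columns are the more relevant ones. Under the design alternative, with at least 90% power, a non-significant primary is also the less likely outcome. Still, the lesion-free endpoint contains the T1 Gd+ lesions, so a true effect on the primary would be expected to carry into it. False secondary claims are therefore a concern chiefly where the primary shows nothing.

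Finally, this is a Phase II trial with standard MRI outcomes, and no effect on participant safety is in question. That limits the weight of the point. It does not remove it, because the sponsor itself chose to promise the control.

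**Conclusion.** The concern holds. The protocol asserts family-wise control over the primary and secondary endpoints, and following the SAP as written does not deliver it for the two secondaries. If each were tested at 0.05 with no true effects, the chance of at least one false secondary claim would be 7.0% to 9.75% for correlations from 0.9 to 0. The chance of a false secondary claim alongside a non-significant primary would be 3.4% to 9.3%. Even at correlation 0.9, the error over all three tests is 8.4%, above 5%. These sizes depend on the assumed level and correlations; the absence of a procedure does not. The primary test at 5%, its power and the sample size are unaffected. The point should be fixed before unblinding.

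**What to change.** Add a paragraph to SAP 5.4.1 before unblinding that sets a fixed sequence at two-sided 0.05, for example in the order already listed:

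1. Total new T1 Gd+ lesions (primary).
2. Total new or enlarging T2 lesions.
3. Proportion free of both lesion types.

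Each test is made only if the previous one is significant; after the first failure, the remaining p-values are reported as nominal. State that the logistic result opens the gate if the primary negative binomial model fails to converge, since SAP 5.3.2 switches models in that case. Holm or Hochberg on the two secondaries, applied only after a significant primary, is an acceptable alternative.

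If strict control is not intended, amend the sentence in Protocol section 9 and the heading of SAP 5.4.1, and label the secondary p-values nominal.

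The first route costs a short SAP amendment and changes neither the sample size nor primary power. The second also changes protocol wording, so the sponsor would have to decide whether it counts as a substantial amendment needing the approvals described in Protocol Appendix A1-1.

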9.1 STATISTICAL HYPOTHESES

The primary purpose of this study is estimation and hypothesis testing regarding the effect of fenebrutinib on the primary endpoint of total number of new T1 Gd+ lesions relative to placebo. Point and interval estimates of the true underlying lesion rate ratio will be presented along with the p-value.

9.2 SAMPLE SIZE DETERMINATION

A sample size of 102 was chosen to ensure at least 90% power to detect a 60% reduction in total number of new T1 Gd+ lesions. This assumes that the placebo arm has 0.7 new lesion per post-baseline scan and assuming 3% dropout by the end of study. Approximately 68 will be randomized to receive fenebrutinib and 34 randomized to receive placebo.

9.3 ANALYSIS SETS

All patients

Efficacy and biomarker endpoints will be *analyzed on all randomized patients*.

Efficacy and biomarker analyses will use all randomized patients grouped by treatment as assigned by randomization.

Safety Population

The Safety Population will include all participants who received any study drug. Patient who received an incorrect medication rather than the one they were randomized will be summarized in the group according to the treatment actually received.

All safety outcome measures will be analyzed using the Safety Population.

PK Population

The PK analysis population will consist of participants with sufficient data to enable estimation of key parameters, with participants grouped according to treatment received.

